6. PLANNED ANALYSIS

6.1. Interim Analysis

No interim analysis is planned.

6.2. Final Analysis

Final analysis will be performed according to the current version of the protocol (version 2 of March 14th, 2023) and to this Statistical Analysis Plan (version 1 of October 10th, 2023), after data cleaning operations and Data Base (DB) Lock will be performed.

The statistical analysis will be performed using SAS 9.4 for Windows (SAS Institute Inc., Cary, NC, USA).

7. SAMPLE SIZE AND STATISTICAL POWER CONSIDERATION

A previous study reported by De-Hita-Cantalejo C, et al 2022 [3], baseline level of TFBUT of 6.23 ± 1.75 in patients with moderate dry eye disease. After 30 days of treatment with tear eyedrops containing hyaluronic acid 0.3%, TFBUT was 8.10 ± 2.06 s. To detect a 25% of increase of TFBUT at Study Termination Visit compared to the baseline (Visit 1) (mean difference 1.56, s.d. 1.91), considering an alpha = 0.01 (two-tailed) and a power of $1 - \beta = 0.80$, 23 patients are required (Wilcoxon signed-rank test). Taking into account an expected dropout of 20%, it is expected to enroll a total of 28 patients.

8. ANALYSIS POPULATIONS

8.1. Screening Failures

Screening failures will be defined as patients who provided informed consent but who were not enrolled randomised. Screening Failures will be summarised and presented by a total count.

More details regarding the patient distribution will be described in the consort figure as reported in paragraph 15.1.

8.2 Total Set

The total set will be defined as all patients who provided informed consent as documented on the ‘Informed Consent’ eCRF page. The total set will be summarized and presented by a total count (without study treatment categorization).

8.3. Intent-to-Treat Population (ITT)

The performance analysis will be performed on the full intent to treat population (ITT) population. The ITT population consisted of all enrolled patients who receive at least one dose of the study experimental product. The patients with no treatment applied at all and the patients who do not have any available data after the first dose of treatment should be excluded from the analysis.

8.4. Per-Protocol (PP) Population

The per protocol set (PPS) will be used for supportive performance analysis. The PPS consisted of patients in the ITT who did not have any major protocol violation.

8.5. Safety Population

The safety population, used for all safety analyses, consisted of all patients who received at least one dose of the medical device.

9. GENERAL ISSUES FOR STATISTICAL ANALYSIS

9.1 Definitions, Derived Variables and Datasets

Variable (CRF)	Variable	Type	Description
md_dispensing_q7; checkcomp_and_mdret_q3.	Treat_time	Continuous	Treatment duration
age	Age	Continuous	Age
sex_at_birth	Sex	Discrete	Sex
race	Race	Discrete	Race
eoq_q3; eoq_q4;	Ext_oc_ex	Discrete	External ocular examination
mh_part1_q1; mh_part1_q1_ongoing; mh_part1_q2; mh_part1_q2_ongoing; mh_part1_q3; mh_part1_q3_ongoing; mh_part1_q4; mh_part1_q4_ongoing; mh_part1_q5; mh_part1_q5_ongoing; mh_part1_q6; mh_part1_q6_ongoing; otherprevious_cdiseases; table_otherprevious_cd1.	Med_hist	Discrete	Medical history
concomitant_q1; concomitant_q2; concomitant_q3;	Conc_med	Discrete	Concomitant medications

Hyalistil Bio PF Mono
Medical device

Study code: 052/SI Hyalistil Bio PF Mono

concomitant_q4.			
tfbut_q2_od; tfbut_q3_od; tfbut_q4_od; tfbut_q2_os; tfbut_q3_os; tfbut_q4_os; tfbut_q5_od_a; tfbut_q5_os_a.	TFBUT	Continuous	Tear film break-up time with fluorescein
cornea_od_totalscore_a; cornea_os_totalscore_a; conjunctiva_od_totalscore_c; conjunctiva_od_totalscore_d; cornea_conjunctiva_os_b_d; cornea_conjunctiva_od_a_c;	NEI_total NEI_cornea NEI_conjunt	Continuous	National Eye Institute Scale
eo5;	BCVA	Continuous	Best Corrected Visual Acuity
sande_q3_severity; sande_q4_frequency; sande_qc_score2;	SANDE_total SANDE_sev SANDE_freq	Continuous	Symptom Assessment in Dry Eye
vasscale_q2; vasscale_cornea_q1; vasscale_cornea_q2; vasscale_cornea_q3; vasscale_cornea_q4; vasscale_cornea_q5;	VAS1 VAS2 VAS3 VAS4 VAS5	Continuous	Degree of satisfaction to the treatment
sensazione_deqs; secchezzaoculare; doloreagliocchi; stanchezzaoculare; pesantezzadellepalpedre; rossoreagliocchi; sensazione_deqs_1; secchezzaoculare_1; doloreagliocchi_1; stanchezzaoculare_1; rossoreagliocchi_1; deqs_q13; deqs_q14; deqs_q15; deqs_3. GES	DEQS_sum_score DEQS_subscale1 DEQS_subscale2	Continuous	Questionnaire about Eye Symptoms and Daily Life
igas_q1	IGAS	Discrete	(Investigator Global Assessment of Safety)

Study code: 052/SI Hyalistil Bio PF Mono

Incident_adverseevent_q1; incident_adverseevents_q2; incident_adverseevent_q3; endofstudy2_q4;	Adv_event_Inc	Discrete	Adverse events/incidents
iop_q2_od; Iop_q2_os;	IOP	Continuous	Evaluation of intraocular pressure
checkcompliance_q1; checkcompliance_q2; checkcompl_and_mdret_q3;	Compliance	Continuous/Discrete	Evaluation of compliance through verification of correct instillation of the medical device

10. STATISTICAL METHODS

Descriptive analysis will be performed by using absolute rate, percentage and frequency tables for qualitative variables.

Normally distributed continuous data will be reported as minimum, maximum, mean and standard deviation, whereas non- normally distributed data as medians and IQR.

Categorical variables will be analyzed by using Yates-corrected chi-square test or Fisher's exact test when appropriate. The McNemar's test will be used to analyze paired nominal data. Differences in endpoints between baseline and different timepoints will be assessed using paired t-test for normally distributed data, whereas the Wilcoxon signed-rank test will be used for non-normally distributed data.

Data distribution will be evaluated through the Kolmogorov-Smirnov test.

A p-value <0.05 will be considered statistically significant.

Analysis will be performed using SAS version 9.4 for Windows (SAS Institute Inc., Cary, NC, USA).

10.1. General Issues for Statistical Analysis

All data will be summarized and listed as appropriate. ~~Performance data will be summarized and listed for the overall population.~~

Performance data will be summarized, listed and described in table for the overall population.

There are no subgroups.

For more details see paragraph 13 and the list and samples of tables, figures and graphs, reported in paragraph 15.

10.2 Definitions, Derived Variables and Datasets

10.2.1 Baseline Values

Study code: 052/SI Hyalistil Bio PF Mono

Data collected at the screening/baseline visit (Visit 1), before the beginning of the treatment, are considered as baseline values.

The last observation carried forward method (LOCF) was used to replace missing data in each performance endpoints.

Baseline and demographic characteristics of the patients will be summarized by using appropriate descriptive statistics.

For more details see paragraph 11.1.

10.2.2 Demographic Data

Demographic data (age, sex, race) were summarized using mean, SD, minimum, maximum, median, lower quartile and upper quartile for continuous variables and number of patients (frequency) and percentage per category for categorical variables.

10.2.3 Duration of Exposure

All patients will be followed from enrolment until study end date, which will occur when, in compliance with the normal clinical practice, the last patient will be patient to the study termination visit (30 days from the first application of study product) (window ± 4 day).

For each patient enrolled, the duration of exposure per patient will be estimated as the number of days between the first and last treatment administration. Mean and SD, minimum and maximum number of days of treatment will be reported.

10.2.4 Treatment Compliance

Treatment duration per patient will be estimated as the number of days between the first and last treatment administration. Absolute rate and percentage of days of treatment will be reported.

Compliance will be estimated as the percentage of administrations given with respect to the administrations planned. Compliance will be also reported categorical as <50%, 50-80% and >80%. In particular:

1. <50% = Poor Compliance
2. 50-80% = Moderate Compliance
3. >80% = Good Compliance

Details by patients about compliance well be reported

10.2.5. Methods for Withdrawals and Missing Data

Reasons for withdrawal will be considered and patients will be entered in the analysis on the basis the reason for withdrawal.

If the primary performance measurement at Visit 2 is missing, it will be imputed with the score at baseline. If the primary performance measurement at Study Termination Visit is missing, it will be imputed with the score at Visit 2, if it is not missing, or otherwise with the score at baseline.

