3.2. Secondary objective

The secondary objectives were:

Clinical Performance

- Evaluation of the change in total score (score from 6 to 33, considering a normal score 0-33) resulting from the sum of the corneal staining score (score from 0 to 15) and conjunctival staining score (score from 0 to 18) with fluorescein using the National Eye Institute Scale (NEI) at Visit 2 (*Day 14 ± 2 of treatment*) and at the Study Termination Visit (*Day 35 ± 4 of treatment*) compared to Visit 1 (*Day 0 of treatment - baseline*);
- Evaluation of the tear film stability per group as objectified by the tear break up time with fluorescein (TFBUT) at Study Termination Visit (*Day 35 ± 4 of treatment*) compared to Visit 2 (*Day 14 ± 2 of treatment*).
- Changes about Best Corrected Visual Acuity (BCVA) measured by the “*Early Treatment Diabetic Retinopathy Study*” (ETDRS) at Visit 2 (*Day 14 ± 2 of treatment*) and Study Termination Visit (*Day 35 ± 4 of treatment*) compared to Visit 1 (*Day 0 of treatment – baseline*).

Patient reported outcomes

- To compare patients reported outcomes (PRO) measures per group, including:
 - Patient's reported symptoms (SANDE) at Visit 2 (*Day 14 ± 2 of treatment*) and Study Termination Visit (*Day 35 ± 4 of treatment*) compared to Visit 1 (*Day 0 of treatment – baseline*).
 - Evaluation of the degree of satisfaction to the treatment reported by patients through the use of the visual analogue scale (VAS) ##, at the Study Termination Visit (*Day 35 ± 4 of treatment*).
 - Assessment of the quality of life (QOL) ### by “Questionnaire about Eye Symptoms and Daily Life” (DEQS) at Study Termination Visit (*Day 35 ± 4 of treatment*) compared to Visit 1 (*Day 0 of treatment - baseline*).

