13.2 Secondary objective

The secondary objectives were:

Clinical Performance

- Changes in NEI score from baseline will be summarized as minimum, maximum, mean,

Study code: 052/SI Hyalistil Bio PF Mono

standard deviation or median and IQR. Paired t-test or Wilcoxon signed-rank test will be used to test the statistical significance of the change from baseline to each timepoints. [Time frame: Visit 1, Visit 2 and Study Termination Visit].

The cornea is divided into five sectors (central, superior, inferior, nasal and temporal), each of which is scored on a scale of 0–3, with a maximal score of 15. Both nasally and temporally, the conjunctiva is divided into a superior paralimbal area, an inferior paralimbal area and a peripheral area with a grading scale of 0–3 and with a maximal total score of 18 for the nasal and temporal conjunctiva.

For a better reading it is also essential not to use an intense illumination beam, which may reduce the contrast and lead to an underestimation of grading.

- Changes in TFBUT from baseline will be reported as minimum, maximum, mean standard deviation or median and IQR. Paired t-test or Wilcoxon signed-rank will be used to test the statistical significance of the change from baseline to each timepoints. [Time frame: Visit 2, and Study Termination Visit].
- Change in the BVCA scores will be summarized as minimum, maximum, mean, standard deviation or median and IQR. Paired t-test or Wilcoxon signed-rank test will be used to test the statistical significance. Details of changes (i.e., difference in BVCA scores between baseline and end of treatment) will be summarized as well. [Time frame: Visit 1, Visit 2 and Study Termination Visit].
- Best Corrected Visual Acuity BCVA was measured using the standard Early Treatment Diabetic Retinopathy Study (ETDRS) acuity chart lighting, and procedures and reported in Best-corrected visual acuity is measured at all trial visits using standard charts, (chart 1 is used for testing the visual acuity of the RIGHT eye; Chart 2 for testing the LEFT eye). Patients should not be allowed to see any of the charts before the examination.

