15. LIST AND SAMPLES OF TABLES, FIGURES AND GRAPHS

The following lists of tables might not be exhaustive. Additional tables can be produced if necessary.

For each comparison of the various quantitative endpoints (visit 2 versus visit 1 and visit 3 versus visit 1) the descriptive statistics of the endpoint at the two visits will first be calculated and then the P-value will be calculated to assess the statistical significance of the difference. This difference will also be reported as a percentage from baseline.

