5 PERFORMANCE DATA (SECONDARY ENDPOINTS)

-NEI Scale ITT population

Table 5.1.1 TOTAL SCORE NEI ITT population (v1) vs (v3)

Table 5.2.1 TOTAL SCORE NEI ITT population (v1) vs (v2)

Table 5.3.1 TOTAL SCORE CORNEA ITT population (v1) vs (v3)

Table 5.3.2 TOTAL SCORE CORNEA ITT population (v1) vs (v2)

Table 5.4.1 TOTAL SCORE CONJUNCTIVA ITT population (v1) vs (v3)

Table 5.4.2 TOTAL SCORE CONJUNCTIVA ITT population (v1) vs (v2)

-TFBUT ITT POPULATION

Table 5.5.1 TFBUT ITT population (v1) vs (v2)

-Questionnaire SANDE ITT population

Table 5.6.1 TOTAL SCORE SANDE ITT population (v1) vs (v3)

Table 5.7.1 TOTAL SCORE SANDE ITT population (v1) vs (v2)

Study code: 052/SI Hyalistil Bio PF Mono

Table 5.8.1 SEVERITY DRYNESS/IRRITATION ITT population (v1) vs (v3)

Table 5.8.2 SEVERITY DRYNESS/IRRITATION ITT population (v1) vs (v2)

Table 5.9.1 FREQUENCY DRYNESS/IRRITATION ITT population (v1) vs (v3)

Table 5.9.2 FREQUENCY DRYNESS/IRRITATION ITT population (v1) vs (v2)

-Questionnaire VAS ITT population

Table 5.10.1 Question "I feel satisfied using this treatment? ", ITT population

Table 5.10.2 Question "With this treatment, I have a feeling of freshness?", ITT population.

Table 5.10.3 Question "With this treatment, I have a feeling of relief?", ITT

Table 5.10.4 Question "This treatment contributed to reduce my pain due to eye dryness?", ITT population

Table 5.10.5 Question "This treatment is comfortable? ", ITT population

Table 5.10.6 Total score VAS, ITT population

-DEQS ITT POPULATION

Table 5.11.1.1 DEQS Summary score ITT population (v1) vs (v3)

Table 5.11.2.1 DEQS Bothersome Ocular Symptoms subscale ITT population (v1) vs (v3)

Table 5.11.3.1 DEQS Impact on Daily Life subscale ITT population (v1) vs (v3)

Table 5.11.4.1 DEQS-GES ITT population (v1) vs (v3)

-IGAS

Table 5.12.1 IGAS ITT populations

-IOP ITT POPULATION

Table 5.13.1 IOP ITT population (v1) vs (v3)

Table 5.14.1 IOP ITT population (v1) vs (v2)

Study code: 052/SI Hyalistil Bio PF Mono

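### Replacing a missed Visit 2 TFBUT with baseline, even when the patient is measured at termination, pulls the planned Visit 1 versus Visit 2 comparison toward zero

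*SAP*

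**What the plan says.** SAP 10.2.5 sets two rules for the primary measurement, TFBUT. For Visit 2: "If the primary performance measurement at Visit 2 is missing, it will be imputed with the score at baseline". For a missing termination value: "it will be imputed with the score at Visit 2, if it is not missing, or otherwise with the score at baseline". Protocol section 23 and the synopsis carry the same two rules. Neither document makes the Visit 2 rule depend on whether a later value exists.

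SAP 10.2.1 goes further than the protocol, which imputes only the primary measurement: "The last observation carried forward method (LOCF) was used to replace missing data in each performance endpoints".

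Three statements bear on which comparisons use a Visit 2 value:

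- SAP 3.2 lists a secondary objective, "Evaluation of the tear film stability per group as objectified by the tear break up time with fluorescein (TFBUT) at Study Termination Visit", compared with Visit 2. The protocol lists it too.
- SAP 13.2 tests the secondary TFBUT endpoint against baseline only: "Paired t-test or Wilcoxon signed-rank will be used to test the statistical significance of the change from baseline to each timepoints".
- SAP 15 describes comparisons of Visit 2 with Visit 1 and of Visit 3 (termination) with Visit 1. Its table list has TFBUT Visit 1 versus Visit 2 (Table 5.5.1), the same contrast for NEI (5.2.1, 5.3.2, 5.4.2) and for SANDE (5.7.1, 5.8.2, 5.9.2), and no table of termination versus Visit 2.

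The secondary tables are for the ITT population only. No observed-data version is planned.

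**The concern.** A patient who skips Visit 2 and returns at Day 35 has a measured on-treatment value. The rule ignores it and enters the pre-treatment reading as the Day 14 reading. The record then shows no change at Day 14, and the whole Day 0 to Day 35 change appears to occur after Day 14.

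The Visit 2 rule also does nothing for the primary endpoint, which compares Visit 1 with termination. If both post-baseline values are missing, the termination rule already falls back to baseline. The Visit 2 rule therefore acts only on comparisons that use Visit 2, and there it inserts values known to come from before treatment. At stake is the Day 14 estimate for TFBUT and, through SAP 10.2.1, for NEI and SANDE. The Day 14 to Day 35 objective is also at stake if it is analysed.

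**Working it through.** **Planning figures.** 25% of 6.23 s is 0.25 × 6.23 = 1.5575, the stated 1.56 s. The stated SD follows from the two visit SDs: √((1.75² + 2.06²)/2) = 1.91 s. With these, alpha 0.01 two-sided and power 0.80, a paired t-test needs 21 patients and the signed-rank test 22 under normality (efficiency 3/π), close to the stated 23. Below, the design change of 1.56 s serves as the termination change d35.

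**Whom the rule reaches.** Protocol 23 admits to the ITT set only patients with a primary post-baseline assessment. SAP 8.3 excludes those with no data after the first dose. A patient in the set with no Visit 2 TFBUT will therefore nearly always have a termination value, so the rule acts almost only on isolated gaps.

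**Bias.** Let m be the share of patients with Visit 2 missing and termination observed, with missingness unrelated to outcome.

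- Visit 2 minus Visit 1 becomes (1 − m) × d14 + m × 0. The bias is −m × d14.
- Termination minus Visit 2 becomes (1 − m)(d35 − d14) + m × d35 = (d35 − d14) + m × d14. The bias is +m × d14.
- Termination minus Visit 1 is unchanged, because both values are observed.

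**Numbers.** The documents give neither m nor d14. Assuming d14 = 1.0 s and d35 = 1.56 s (true later gain 0.56 s):

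| Missed Visit 2, of 28 | m × d14 | Day 14 change (true 1.00 s) | Later gain (true 0.56 s) |
|---|---|---|---|
| 1 | 0.04 s | 0.96 s | 0.60 s |
| 3 | 0.11 s | 0.89 s | 0.67 s |
| 5 | 0.18 s | 0.82 s | 0.74 s |

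Over other assumptions, with 1, 3 or 6 of 28 missing, the bias is 0.03, 0.08 or 0.17 s if d14 = 0.78 s (half the design effect), and 0.06, 0.17 or 0.33 s if d14 = 1.56 s (all of it).

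**Effect on tests.** A simulation used 20,000 runs, 28 patients, SD 1.91 s at each visit, correlation 0.5 and a paired t-test at 0.05.

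- *Termination versus Visit 2, no true later gain, d14 = 1.56 s.* The rule gave rejection rates of about 5%, 6% and 12% for 1, 3 and 6 missing. Observed pairs gave about 5% throughout.
- *Visit 2 versus Visit 1, d14 = 0.78 s.* The rule gave 54%, 50% and 44%. Observed pairs gave 54%, 50% and 45%. (The observed-pair rates are those for termination versus Visit 2, which in this set-up has the same mean and variance.) In these settings the t-test hardly changes and the damage is to the estimate.

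**Offset.** If a share q of patients has termination carried from Visit 2, their later gain is set to zero, and the net bias in the later gain is m × d14 − q × (d35 − d14). With 3 of 28 of each type and d14 = 0.78 s, this is 0.084 − 0.084 = 0. With d14 = 1.0 s it is 0.107 − 0.060 = 0.047 s.

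**The case against.** The strongest reply is that the rule harms little that the plan will report.

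- A reader might infer that the study will publish an inflated Day 14 to Day 35 gain. The documents do not support that. The contrast is a stated objective, but neither SAP 13.2 nor SAP 15 gives it a test or a table. The inflation also needs a positive d14 and can be offset as shown.
- A reader might infer that the primary result is biased. It is not, for these patients.
- In the planned Visit 1 versus Visit 2 tables the bias works against showing an effect.
- The inputs are assumed. The only attrition figure, 20% dropout, concerns patients who leave, not those who miss one visit and return. With one missed visit the bias is about 0.04 s against a planning SD of 1.91 s.
- The carry-forward sentence in SAP 10.2.1 is a single line under the heading for baseline values. It does not say whether baseline itself may be carried. It is tempting to conclude that a missed termination DEQS will be scored as no change, but the text does not settle that.

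All of this limits the point, and none of it removes it. At Visit 2 the only earlier scheduled value is baseline, so carry-forward there can mean nothing else. A bias toward zero is still a bias in a planned estimate, and no planned output would reveal it. Possible cancellation in the later gain does not justify the rule.

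**Conclusion.** The point stands for the Visit 2 comparisons of secondary endpoints. An isolated missed Visit 2 is filled with a pre-treatment value, and the mean Day 14 change is pulled toward zero by m × d14: about 0.04 to 0.18 s for 1 to 5 of 28 patients if the true Day 14 change is 1.0 s. This assumes missingness unrelated to outcome. With one or two missed visits the effect is small. For NEI and SANDE the mechanism is the same on the SAP 10.2.1 wording, but the documents offer no figures with which to size it. The termination versus Visit 2 consequence is conditional on that objective being analysed. The change is worth making because the distortion comes entirely from a written rule that the primary endpoint does not need.

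**What to change.** In SAP 10.2.5, and in the matching text of Protocol 23 and the synopsis, state that a missing Visit 2 value is not imputed when a later value is observed. Estimate Visit 2 minus Visit 1 and termination minus Visit 2 either from observed pairs or from one repeated-measures model with visit as a factor. Apply the same to NEI and SANDE at Visit 2. Add a table for termination versus Visit 2, so that the stated objective has an output. Keep the carried-forward version as a sensitivity analysis. Carry-forward for patients who drop out is a separate trade-off, and this point does not call for deleting it across all endpoints.

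Cost: a few lines of text and a routine SAS run. The number of patients will differ slightly between visits. The protocol edit needs a written, signed amendment sent to the ethics committees. The SAP is dated October 10th, 2023, after the last patient's last visit on August 3rd, 2023, so the change should be dated, justified and made before database lock, with both versions reported.

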	
evaluations on both eyes of the individual patient.
 
In the case that both eyes are affected by ocular dry eye, the statistical analysis will be performed considering the eye with the lowest level of TFBUT score “worse eye”. If the level of TFBUT score at baseline is the same in both eyes, then the eye with the highest level of NEI score will be designated as the “worse eye.”
 
If the level of NEI score at baseline is the same in both eyes, then the right eye will be designated as the “worse eye.”
 
#The primary end point will be evaluated on the PP population and also in ITT population.

STATISTICS	
Sample size estimate
 
A previous study report baseline level of tear film break-up time with fluorescein (TFBUT) of 6.23 ± 1.75 at baseline, to detect a 25% increase of TFBUT at the Study Termination Visit compared to baseline (Visit 1) (mean difference 1.56, sd 1.91), with an alpha=0.01(two-tailed) and a power $(1 - \beta)$ of 0.80, 23 subjects are required (Wilcoxon signed-rank test). Considering a dropout of 20%, it is expected to enroll a total of 28 subjects.
 
Statistical analysis
 
Descriptive analysis will be performed by using absolute rate, percentage and frequency tables for qualitative variables.
 
Normally distributed data will be reported as minimum, maximum, means and standard deviations, whereas non-normally distributed data as medians and interquartile range (IQR).
 
To compare qualitative variables for not-paired data will be used the Chi-square test with Yates corrections or Fisher's exact test when appropriate and the McNemar's test for paired data.
 
Differences in endpoints between baseline and different timepoints will be assessed using paired t-test for normally distributed data, whereas the Wilcoxon signed-rank test will be used for non-normally distributed data.
 
Data distribution will be tested by using the Kolmogorov-Smirnov test. A p-value <0.05 will be considered statistically significant.
 
All the Analysis will be performed using SAS version 9.4 for Windows (SAS Institute Inc., Cary, NC, USA).
 
Analysis set
 
All patients enrolled will be included in the safety population.
 
All patients enrolled having a primary post-baseline -performance assessment will be included in the ITT population.
 
If the primary performance measurement at Visit 2 is missing, it will be imputed with the score at baseline. If the primary performance

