22.5 Insurance Policy

As the study is non-interventional, there is no need for insurance policies in addition to those already provided for normal clinical practice.

22. Subject Compliance

The Subjects' compliance will be monitored by study staff during visits and evaluated by the Investigator. Any subject found not to follow pre-study directions or to be non-compliant, will be withdrawn from the study. Details of the reason for removal of subjects will be recorded and reported.

23. Statistic

Sample size estimate

A previous study report baseline level of TFBUT of 6.23 ± 1.75 in patients with moderate dry eye disease. After 30 days of treatment with tear eyedrops containing hyaluronic acid 0.3%, TFBUT was 8.10 ± 2.06 s [20]. To detect a 25% of increase of TFBUT at Study Termination Visit compared to the baseline (Visit 1) (mean difference 1.56, s.d. 1.91), considering an alpha = 0.01 (two-tailed) and a power of $1 - \beta = 0.80$, 23 subjects are required (Wilcoxon signed-rank test). Taking into account an expected dropout of 20%, it is expected to enroll a total of 28 subjects.

Analysis set

All patients enrolled will be included in the safety population.

All patients enrolled having a primary post-baseline performance assessment will be included in the PP population and ITT population.

If the primary performance measurement at Visit 2 is missing, it will be imputed with the score at baseline. If the primary performance measurement at Study Termination Visit is missing, it will be imputed with the score at Visit 2, if it is not missing, or otherwise with the score at baseline.

All patients of the ITT population who did not have any major clinical investigation plan deviation will be included in the PP population.

The analysis of safety endpoints will be performed in the safety population. Analysis of performance endpoints will be performed on the ITT population. The analysis of primary endpoint will be performed on the PP population but this later will be repeated in the ITT population.

Statistical Methods

Descriptive analysis will be performed by using absolute rate, percentage and frequency tables for qualitative variables.

Normally distributed continuous data will be reported as minimum, maximum, mean and standard deviation, whereas non- normally distributed data as medians and IQR.

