10.2.7. Premature Discontinuation

Dropout patients will be defined as patients who prematurely discontinued the study. Patients who had stopped the study treatment but were still being followed in the study were not considered as dropouts.

All data available until the premature discontinuation will be taken into account.

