11.2 Protocol Deviations

Protocol deviations will be registered in the monitoring visits reports, performed during the study. Protocol deviations will be described in Table and in Listing.

The number and percentage of patients with any, major, and minor protocol deviations will be summarized for all enrolled patients. Major protocol deviations are defined as protocol deviations that may impact primary performance endpoint; other protocol deviations are classified as minor. Protocol deviations will be assessed prior to database lock and unmasking. The number and percentage of patients with any protocol deviation will also be summarized for the following categories: Informed Consent, Inclusion / Exclusion, Instillation of investigational product. Improper Protocol Procedures at Site, Site's Failure to Report Serious Adverse Event (SAE) / AE, Visit Out of Window, patient's Use of Prohibited Concomitant Medication, and Other. A patient listing will be provided that includes the date, description of each deviation and the classification of whether the deviation was judged to be major or minor.

The Sponsor will consider the following criteria for exclusion of a patient from the PPS:

- Impossibility to assess the compliance with investigational medical product application (patients who have not returned the amount of used single dose containers and/or empty/unused medical device boxes);
- Missing primary performance data;
- Failure to satisfy any inclusion/exclusion criteria;
- Intake of prohibited medications.

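### Protocol and SAP define different ITT sets, and each leaves out some or all of the early dropouts whom the imputation rule would count as no change

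*SAP*

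**What the plan says.** **Imputation.** SAP 10.2.5, Protocol section 23 and the protocol synopsis carry the same rule. "If the primary performance measurement at Visit 2 is missing, it will be imputed with the score at baseline". A missing termination value takes the Visit 2 value where there is one, "or otherwise with the score at baseline".

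**ITT in the protocol.** Section 23 (Analysis set): "All patients enrolled having a primary post-baseline performance assessment will be included in the PP population and ITT population". The synopsis: "All patients enrolled having a primary post-baseline -performance assessment will be included in the ITT population".

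**ITT in the SAP.** Section 8.3 takes enrolled patients who received a dose, but adds that "patients who do not have any available data after the first dose of treatment should be excluded from the analysis".

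**PP set in the SAP.** Section 11.2 lists "Missing primary performance data" among the criteria for exclusion.

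**Withdrawals.** SAP 10.2.5 opens by making entry into the analysis depend on the reason for withdrawal, and gives no rule. SAP 10.2.1 applies last observation carried forward (LOCF) to each performance endpoint. SAP 10.2.7 says: "All data available until the premature discontinuation will be taken into account". Protocol section 8.1 asks for an Early Termination Visit where possible. The imputation rule does not mention that visit.

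**The concern.** A rule that assigns the baseline value to a patient with no later measurement is a deliberate choice to count that patient as no change. It works only if the analysis set keeps such patients. The protocol's set requires the very measurement whose absence triggers the rule. The SAP's set is wider but still drops patients with nothing recorded after dosing.

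The primary endpoint is expressed as a 25% increase, so the estimated percentage is a main result. Worsening and adverse reactions are listed withdrawal reasons (Protocol section 8), so patients lost before Visit 2 may differ from completers. If they did worse, leaving them out inflates the estimate. Apart from bias, two statisticians working from the two documents could produce different ITT tables from the same data.

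**Working it through.** **1. The definitions applied to each kind of dropout**

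| Patient | Protocol ITT | SAP ITT | Value under SAP 10.2.5 |
|---|---|---|---|
| No data after first dose | Out | Out | Baseline, but never applied |
| Some post-dose data (e.g. an adverse event), no TFBUT | Out | In | Baseline, change = 0 |
| Only later TFBUT is from an Early Termination Visit before Visit 2 | In | In | Not stated: baseline if 10.2.5 is read alone, the observed value under LOCF |
| TFBUT at Visit 2, none later | In | In | Visit 2 carried forward |

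The documents disagree on the second row. The first row is lost under both. The third row is the only route by which the baseline step can operate under the protocol. The PP analysis does not restore the first two rows, because missing primary data is an exclusion criterion there.

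**2. The plan's own figures (SAP section 7)**

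- Inputs: baseline 6.23 s, mean change 1.56 s, SD of change 1.91 s, two-sided alpha 0.01, power 0.80, 23 required, 20% dropout, 28 enrolled.
- Planned increase: 1.56 / 6.23 = 25.0%.
- Effect size: 1.56 / 1.91 = 0.817. The paired t-test needs 21 patients. The signed-rank test, with relative efficiency 3/π, needs 22, and its power at 23 is 0.827. The stated 23 is reproduced within one patient.
- Enrolment: 23 × 1.2 = 27.6, rounded up to 28, matches the plan. Dividing by 0.8 gives 28.75, or 29.

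**3. Effect on the estimated increase**

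Assume that completers average +1.56 s and that k of 28 patients have no post-baseline TFBUT. Excluding them leaves 25.0%. Counting them as no change gives

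increase = 1.56 × (28 − k) / 28 / 6.23

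- k = 1: 1.56 × 27/28 = 1.50 s, 24.1%
- k = 2: 1.56 × 26/28 = 1.45 s, 23.3%
- k = 5: 1.56 × 23/28 = 1.28 s, 20.6%

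The case k = 5 is close to the whole planned dropout (0.20 × 28 = 5.6) occurring before any TFBUT, so it is near the upper end.

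Protocol section 4 replaces withdrawn subjects. If replacement brings completers up to 28, the formula becomes 1.56 × 28 / (28 + k) / 6.23. This gives 24.2%, 23.4% and 21.2% for k = 1, 2 and 5, so the picture is much the same.

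**4. Effect on the test**

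In simulation (changes normal with mean 1.56 and SD 1.91, k = 5, 20,000 runs), paired t-test power is 0.850 with these patients excluded and 0.844 with them imputed at alpha 0.01. At alpha 0.05 it is 0.963 and 0.962. A signed-rank test that discards zero differences ignores the imputed patients altogether.

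**The case against.** The other side has several good points, and they limit how far the concern goes.

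- A reader might infer that the baseline step can never run under the protocol. The text does not support that. The protocol does not say at which visit the post-baseline assessment must occur, so a patient whose only later TFBUT came from an Early Termination Visit qualifies. If that value is not treated as the termination value, the baseline step applies.
- A reader might infer that patients stopping for intolerance or worsening are the ones removed. Under the SAP wording, a recorded adverse event can count as post-dose data and keep such a patient in. The SAP exclusion mainly reaches patients who never return, whose outcome is unknown. Upward bias is therefore possible but not shown.
- A reader might infer that an older value will replace a later observed one. SAP 10.2.1 and 10.2.7 point the other way, and both documents introduce the Early Termination Visit within the termination visit section. The gap is that the rule is silent, not that it forbids using the value.
- One early dropout takes the illustration below 25% only because completers were set at 25.0%. The SAP's mock tables test the change against zero, and no decision rule tests 25%.

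What stands is that the ITT definitions differ, that neither fully fits the imputation rule, and that entry by withdrawal reason has no criterion.

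**Conclusion.** The concern holds as an inconsistency between the analysis sets and the imputation rule, with a possible upward bias in the estimated TFBUT increase. Under the protocol the no-change step is almost empty. Under the SAP it covers only patients with some post-dose data but no TFBUT.

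The size depends on two assumptions: that completers average the planned gain, and how many patients have no post-baseline TFBUT, which the documents do not give. For one to five such patients of 28, the difference from the exclusion figure of 25.0% is about 0.9 to 4.4 percentage points (25.0 − 24.1 and 25.0 − 20.6). Its direction as a bias rests on early dropouts having done worse than completers. The test of change against zero is hardly affected, so this is a matter of estimation and of clear definition, not of significance. It should be corrected.

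**What to change.** - Use one ITT definition in both documents: all enrolled patients with at least one dose and a baseline TFBUT, with no post-baseline requirement.
- Delete the sentence in SAP 10.2.5 that makes inclusion depend on the reason for withdrawal.
- State the order of values for the termination time point: Termination, then Early Termination Visit, then Visit 2, then baseline.
- Report how many patients were imputed with baseline, and give the percentage increase with and without them.
- State that ITT is the set in which these patients count, because the SAP's PP set excludes missing primary data.

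A zero-retaining signed-rank test or a count of patients reaching 25% would be a matter of preference and is not needed here.

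The cost is wording in two documents and one additional summary. No new data are required. The reported increase may be slightly smaller.
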